Medications are a first-line treatment for smoking cessation in non-pregnant smokers and could enhance smoking cessation rates during pregnancy [2]. Nicotine replacement therapies (NRTs) aim to replace the nicotine usually obtained by smoking, thereby relieving cravings and withdrawal symptoms [24,25]. Compared to placebo, the odds ratio [OR (95% CI)] of abstinence with nicotine gum is 1.5 (1.2-1.7), with the patch it is 1.9 (1.7-2.1), with the inhaler it is 2.1 (1.5-2.9), and with the nasal spray it is 2.3 (1.7-3.0). Bupropion SR, a non-nicotine medication that inhibits the neuronal reuptake of dopamine and norepinephrine [26], has an OR of 2.0 (1.8-2.2). Varenicline, an $\alpha_4\beta_2$ nicotinic receptor partial agonist [27], has an OR of 3.1 (2.5-3.8). All of these medications are effective for this indication and none is preferred for smoking cessation. The utility of any treatment in an individual patient depends on the safety, tolerability, and perceived helpfulness of the agent.

The use of medication could be particularly beneficial in enhancing quit rates during pregnancy. Some nicotine withdrawal symptoms (e.g., irritability, anxiety, difficulty concentrating, insomnia, restlessness, increased appetite, depressed mood, drowsiness) are also commonly experienced during pregnancy [28]. Because these symptoms are present in pregnant smokers before the initiation of cessation, it may be more difficult for these women to quit because of the additional symptoms of withdrawal [23]. Further, the clearance of nicotine is accelerated during pregnancy, so pregnant smokers may need higher doses of replacement therapy than non-pregnant smokers to optimize efficacy [29]. Finally, pregnancy is associated with markedly elevated levels of progesterone, which is postulated to contribute to heightened withdrawal during the late luteal phase of the menstrual cycle [30]. Consequently, medication may be especially efficacious for smoking cessation in pregnant smokers. Studying the risk/benefit profile of different medications is also important since surveys suggest that 10-30% of practitioners prescribe or recommend NRT for pregnant smokers [31, 32]. ***Medications are safe and effective for smoking cessation in non-pregnant smokers. Research is needed to establish their efficacy and safety in pregnant smokers.***

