Evidence that these biomarkers are mediators of pregnancy outcomes that are affected by smoking has important implications for other pharmacotherapy studies in pregnant smokers by providing surrogate measures of potential risk [46] or in studies of reduced-exposure products (e.g., e-cigarettes, smokeless tobacco) that may be used by pregnant women. Since the FDA has recently been authorized to regulate tobacco products [56] there is likely to be heightened interest in biomarkers of tobacco product risk, particularly in vulnerable populations.

3. Hypotheses, aims and objectives:

Hypothesis 1:

We hypothesize that the nicotine inhaler compared to placebo inhaler will double the 7-day point prevalence abstinence rates (confirmed by exhaled CO) at 32-34 weeks gestation and will reduce the number of cigarettes smoked per day (CPD).

Aims / objectives 1:

To examine the efficacy of the nicotine inhaler compared to a matched placebo for smoking cessation and reduction among pregnant smokers.

Hypothesis 2:

- a) The nicotine inhaler will yield lower cotinine concentrations than placebo at 32-34 weeks gestation.
- b) Infants born to mothers in the NRT group will have higher birth weights and greater gestational age than infants born to mothers randomized to placebo. 2c) Fewer nicotine-treated subjects will deliver a low birth weight (<2500 grams) or a preterm (<37 weeks) infant than those in the placebo group.

Aim/Objective 2:

To compare the nicotine inhaler with placebo on safety measures which include a) overall nicotine exposure (i.e., serum cotinine) and b) birth outcomes (i.e., birth weight and gestational age).

Hypothesis 3: Pregnant women who are heavier smokers (i.e., ≥ 10 cigarettes/day) will be less able to quit with behavioral treatment alone than lighter smokers and the inhaler will increase cigarette abstinence more in heavier smokers.

Aim/Objective 3: To identify factors that determine which women benefit most from the use of nicotine inhaler for smoking cessation during pregnancy

Hypothesis 4: We hypothesize that birth weight will be negatively correlated with CPD and exhaled CO at the end of pregnancy, and that smoking cessation or reduction in the third trimester will explain the effect of treatment group on birth weight. We will also explore the interrelations among birth outcomes, tobacco exposure, and other promising biomarkers.

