Subjects who are eligible and wish to participate will be asked to provide written informed consent before any other information is obtained. Potential subjects 16 and 17 years of age enrolled in CT will require parental consent. After the subject gives informed consent, basic inclusion/exclusion criteria will be assessed. If there are questions regarding the appropriateness of the subject's study participation, eligibility will be reviewed by the study nurse and physician prior to randomization. Given the young age of the population, a proportion will be adolescent, which is responsive to the NIH policy concerning pediatric populations.

Screening Procedures and who will perform them: A study recruiter will accept study referrals, and perform screening procedures. If the study recruiter not available to speak with a referred potential subject, the study nurse or physician may obtain consent and perform screening procedures.

Screening procedures will include consent signing, assessing inclusion/exclusion criteria, and other contact information. The following questionnaires/assessments will be obtained:

Nicotine Replacement for Smoking Cessation during Pregnancy

1. **Demographics:** Age, education, race/ethnicity, income, and type of insurance (public or private),
2. **Smoking history:** We will inquire about past and current smoking, including CPD currently and prior to pregnancy, intention to quit, partner smoking, motivation to quit and number of years of smoking [20, 71]. We will also evaluate prior use of medication to stop smoking and other drugs, including symptoms of other drug abuse or dependence. Smoking social networks will be assessed with items on the smoking status of partner and friends, the number of household smokers, perceived support for staying abstinent and the composition of the household (age and relationship to the subject) [72]. The Fagerstrom Test for Nicotine Dependence [70], a 6-item scale (internal consistency = 0.61), will be used to measure dependence on nicotine.
3. **Screening medical and obstetrics history** will include the number of pregnancies, previous pregnancy outcomes (preterm, term, living, abortions), and information on any current pregnancy problems or underlying medical disorders (e.g., diabetes or HIV infection). Current and past drug abuse history will be recorded. Ongoing medications will be recorded.
4. **Vital signs** (blood pressure, pulse) and **weight** will also be recorded.

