4. **Exhaled carbon monoxide (CO) measurement and Nicotine Use survey** (which assesses any smoking last seven days and since the last study visit and use of other smoking cessation aids)
5. **Vital Signs** (blood pressure and heart rate) and **Weight** will be obtained.
6. **Adverse Effects Inhaler:** Subjects will rate potential adverse effects (cough, throat irritation, rhinitis, and mouth irritation, which have been noted in other nicotine inhaler studies [6, 40, 66]) on a 4-point scale: 0=absent, 1=mild, 2=moderate, and 3=severe. Other AE's will also be recorded and severity rated. This will be done before the subject is administered treatment so we have a baseline to compare other visits.
7. **Concomitant Medication:** Subjects will be asked about their current medication use, including any prescription medication, over the counter medication, supplement, and/or vitamins.
8. **The Minnesota Nicotine Withdrawal Scale (MNWS)** measures symptoms of tobacco withdrawal on a scale of 0 (not present) to 4 (severe) [24]. We will calculate a total score and a score excluding craving to evaluate withdrawal symptoms during cessation.
9. **Release of Information:** A release of information will be obtained at the baseline visit so the study physicians are able to obtain delivery records if the participant will deliver at a hospital other than HH or BMC.
10. **Counseling:** There are 4 primary goals in the initial counseling session: (1) establishing a rapport with the patient, (2) functional analysis of smoking including a review of self-efficacy in various situations, (3) increasing motivation and confidence to quit smoking (using techniques described in the manual), (4) helping the patient to set and prepare for a quit date.

The study nurse provides 35 min of smoking cessation counseling. Subjects will be given "Need Help putting out that Cigarette?" a booklet available for purchase through the American College of Obstetrics and Gynecology. This booklet is written in English or Spanish, is at a 6th grade reading level, provides information about smoking in pregnancy, and outlines steps to prepare to quit and stay quit during pregnancy. The nurse will use responses to the self efficacy questionnaire and diary to help subjects recognize high-risk situations and develop specific strategies to deal with them. The treatment manual describes four primary sources that influence

Nicotine Replacement for Smoking Cessation during Pregnancy

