Aim 3: In our completed study, the effect of nicotine gum appeared to depend on cigarettes per day during the pretreatment period. For light smokers, the cessation rates were 18% and 21% for the control and nicotine groups, respectively, while for heavy smokers the rates were 0% and 15%, respectively. Since a similar effect in a sample of 150 women would provide power=0.80, using a two-sided $\alpha=0.05$, our proposed sample of 360 pregnant smokers will provide more than adequate power to detect the effect.

Aim 4: is exploratory and no sample size was calculated.

Explain on what basis it is reasonable to assume that the sample size will be obtained:

Recruitment will take place over 39 months, requiring enrollment of approximately 9 subjects per month. In our previous study, we had an on-site recruiter at each site (Baystate and Hartford Hospital) and were able to screen 3 pregnant smokers and enroll 2 subjects/week (i.e.,1 subject/site). We will also recruit from CHS in Hartford, where we expect to recruit 1 subject/month. Recruitment sites will be provided with materials designed to raise awareness of the study, including posters and brochures to be displayed prominently in all clinic areas. We will also encourage referrals from clinicians in the surrounding areas at each site, and recruit through newspapers and maternity magazines. Based on our history of recruitment, we are confident that we can reach the proposed recruitment goal.

Subject characteristics:

- Age: **at least 16 years of age**
- Ethnicity: **Hispanic and non-Hispanic. All race and ethnic groups will be eligible**
- Gender: **F**
- Other characteristics - (e.g. primary language etc.): **English or Spanish speaking**

Inclusion Criteria:

- a) smoking at least 5 CPD for the preceding 7 days
- b) previous attempt to quit smoking during pregnancy by self report
- c) 13-26 weeks gestation
- d) at least 16 years of age
- e) able to speak English or Spanish;
- f) intent to carry pregnancy to term; and
- g) stable residence

Exclusion criteria:

Nicotine Replacement for Smoking Cessation during Pregnancy

- a) current drug or alcohol abuse or dependence (other than methadone maintenance)
- b) twins or other multiple gestation
- c) unstable psychiatric disorder
- d) unstable medical problems (e.g., pre-eclampsia, threatened abortion, hyperemesis gravidarum)
- e) known congenital abnormality.

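### No visible eligibility criterion bars current users of other nicotine products or cessation medicines, which can dilute the nicotine-versus-placebo contrast and blur the cotinine reference.

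*Combined protocol and SAP*

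**What the plan says.** The protocol lists seven inclusion and five exclusion criteria. The exclusions cover "current drug or alcohol abuse or dependence (other than methadone maintenance", multiple gestation, unstable psychiatric disorder, unstable medical problems and known congenital abnormality. On smoking, a woman must be "smoking at least 5 CPD for the preceding 7 days" and report a "previous attempt to quit smoking during pregnancy by self report". No visible section contains a list of prohibited medicines or a washout rule.

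The plan does record other products. At screening (smoking history) it states: "We will also evaluate prior use of medication to stop smoking and other drugs". The baseline section describes the Nicotine Use Survey as one "which assesses any smoking last seven days and since the last study visit and use of other smoking cessation aids". The timeline table schedules the survey at every visit, and concomitant medication from screening to Visit 6. The data-analysis section does not say what follows when use is reported.

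The background makes such use plausible. Section A.2 reports surveys suggesting that "10-30% of practitioners prescribe or recommend NRT for pregnant smokers". Section A.3 mentions products such as "e-cigarettes, smokeless tobacco) that may be used by pregnant women".

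Appendix A (procedures to minimise risks, item 4) treats baseline serum cotinine as the level obtained while smoking. It counts an on-treatment value more than 40% above that level as increased nicotine exposure.

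**The concern.** In a placebo-controlled trial of nicotine replacement, the control group should not already be receiving nicotine replacement by another route. As written, a woman who smokes 5 cigarettes a day and wears a nicotine patch meets the criteria and can be assigned to placebo. Three things are affected:

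- **The abstinence contrast (Aim 1).** If another product helps its users quit, the placebo rate rises towards the inhaler rate and the difference shrinks. Even allocation of users does not prevent this.
- **The cotinine comparison (Hypothesis 2a, Aim 2.a).** The protocol describes cotinine as a measure of overall nicotine intake, so it does not identify the source. Section A.3 names anabasine and anatabine as markers of tobacco exposure, but the listed assays do not include them.
- **The cotinine reference in Appendix A.** Its stated purpose is that exposure on treatment should not exceed what the woman usually gets from smoking. If another product contributes to the baseline value, the reference lies above the smoking-only level.

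The gap also sits awkwardly with section A.2.c. There an intermittent product is chosen to limit nicotine exposure, and adding bupropion or varenicline is called undesirable in women on antidepressants.

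**Working it through.** **1. The plan's own figure.** Inputs from the sample-size section, Aim 1: p1 = 0.149 (placebo), p2 = 0.269 (inhaler), two-sided alpha 0.05, power 0.80, 1:1 allocation. With p̄ = (0.149 + 0.269)/2 = 0.209:

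- n per arm = [1.960·√(2·0.209·0.791) + 0.842·√(0.149·0.851 + 0.269·0.731)]² / 0.120² = (1.960·0.5750 + 0.842·0.5687)² / 0.0144 ≈ 179.03, rounded up to 180.
- Power at 180 per arm = Φ[(0.120·√180 − 1.960·0.5750)/0.5687] = Φ(0.849) = 0.802.

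The stated 180 per arm and power of 0.80 reproduce.

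**2. Dilution of the abstinence contrast.** The share f of women using another product is not in the documents, so 5, 10 and 20% are assumptions. If placebo-arm users quit at rate q, the placebo rate is (1 − f)·0.149 + f·q. The inhaler arm is held at 0.269. Two values of q are used:

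- 0.269, meaning the other product works as well as the inhaler is planned to.
- 0.18, the rate with nicotine gum at 32-34 weeks in the investigators' earlier trial (section A.2.b).

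| f | Placebo rate, q = 0.269 | Power | Placebo rate, q = 0.18 | Power |
|---|---|---|---|---|
| 0% | 0.149 | 0.802 | 0.149 | 0.802 |
| 5% | 0.155 | 0.756 | 0.151 | 0.791 |
| 10% | 0.161 | 0.705 | 0.152 | 0.779 |
| 20% | 0.173 | 0.594 | 0.155 | 0.754 |

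Example, f = 10% and q = 0.269: the placebo rate is 0.9·0.149 + 0.1·0.269 = 0.161, the difference is 0.108, and p̄ = 0.215. Power = Φ[(0.108·√180 − 1.960·√(2·0.215·0.785))/√(0.161·0.839 + 0.269·0.731)] = Φ(0.539) = 0.705.

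**3. The cotinine reference.** Let a share s of baseline cotinine come from another product. The smoking-only level is then (1 − s) times the baseline value, and the 40% limit equals 1.40/(1 − s) times that level:

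- s = 10%: 1.40/0.90 = 1.56
- s = 20%: 1.40/0.80 = 1.75
- s = 30%: 1.40/0.70 = 2.00

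The values of s are assumptions. With s = 0 the limit is 1.40 times the smoking-only level, as intended.

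**The case against.** Several points against the concern have force.

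- **Screening would often reveal use.** Prior cessation medication, other aids and current medicines are all asked about before randomisation, and a study obstetrician signs off each entry. This stands in part. Staff may notice a patch user, but the sign-off states no criterion on the matter, so decisions could differ between sites.
- **Randomisation balances users.** This stands. A reader might infer that the placebo arm alone is contaminated and the comparison biased. The documents do not support that: users fall in both arms in expectation, although this is not one of the three urn-balancing variables.
- **Full benefit is pessimistic.** This stands. These women still smoke at least 5 cigarettes a day despite the other product. The placebo-controlled pregnancy trials cited in section A.2.b show small, non-significant differences (18% against 14.9% with gum) or none (28% against 25% with patch). Hence the second power column.
- **Prevalence is unknown.** This stands. The 10-30% is a share of practitioners, not of pregnant smokers. The e-cigarette remark concerns implications for other studies. The inclusion criterion requires a past quit attempt, not current use of an aid.
- **E-cigarette users may seem to be false quitters.** A reader might infer this because abstinence is confirmed by exhaled carbon monoxide alone. The endpoint is abstinence from cigarettes, so a woman who has stopped smoking while using another nicotine source is validly abstinent, as inhaler users are.
- **Consent pages were not available.** They might carry an instruction about other products, so the finding is limited to the visible text.

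**Conclusion.** The gap is real. No visible criterion bars current users of other nicotine products or cessation medicines, and no rule says how recorded use is handled. Later analysis can describe such women but cannot undo their enrolment.

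The expected harm is dilution and noise. Over assumed shares of 5 to 20%, power lies between 0.756 and 0.594 with full benefit, and between 0.791 and 0.754 with the gum rate, against 0.802 planned. Both ranges hold the inhaler arm at 26.9%. If the true share is near zero, so is the loss. The planned sample size is not in error.

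Two stronger readings of the cotinine issue do not hold. A reader might infer that baseline cotinine does not come from smoking; because every participant smokes at least 5 cigarettes a day, it always does in part. A reader might also infer that any rise in total exposure would escape notice. A rise of more than 40% above the woman's actual baseline total is still flagged; what can be missed is a rise relative to her smoking-only level.

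**What to change.** Add one exclusion: use, in the 7 days before baseline, of any other nicotine-containing product (nicotine replacement, e-cigarette, smokeless tobacco), or of bupropion or varenicline for smoking cessation. The window matches the 7-day smoking criterion. Judge it from the Nicotine Use Survey and the concomitant-medication record, both already scheduled at screening and baseline. First confirm that the survey captures e-cigarettes and smokeless tobacco, since the protocol describes it only as covering "use of other smoking cessation aids".

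The exclusion does not reach products started after randomisation. So also pre-specify a sensitivity analysis of the abstinence and cotinine outcomes that uses the product use recorded at later visits.

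The cost is one line in the criteria, a short addition to the analysis section and some extra screen failures. The planned sample size does not change.

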during the first 6 weeks of active treatment, it is unlikely that she will quit during the medication taper. Consequently, at visit 5 (6 week visit), subjects who have not quit smoking (7 day point prevalence abstinence confirmed with exhaled carbon monoxide measurement) will be discontinued from medication treatment and reminded to return all study medication at the next scheduled visit.

Recruitment: We will recruit 360 pregnant women from patients seeking care at the Women's Health Ambulatory Clinic located at Hartford Hospital (HH) or the Wesson Women's & Infants' Unit at Baystate Medical Center (BMC) and Community Health Services (CHS) in Hartford. Study visits will occur at either Hartford hospital (referrals from HH clinic, CHS, or the surrounding greater Hartford area) or Baystate Medical Center (referrals from Wesson Women's Clinic and Baystate Maternal Fetal Medicine Clinic). Baystate will also accept referrals from several Baystate Health Medical practices in other locations, including Baystate Midwifery and Women's Health ([name]); Baystate Wesson Women's Group ([name]); Baystate Mary Lane (Ware, MA), Women's Health Associates and Baystate Wing (Ludlow, MA and Palmer, MA). Study visit will occur at either Baystate Medical Center or at one of the above locations, depending on the subject's preference.

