Study staff will also accept referrals from each of the practice locations noted above. In addition, potential participants may refer themselves to the study by contacting study staff directly or by leaving their contact information on the study voicemail. These individuals will be contacted to determine if they are interested in participating in the study. For the convenience of our subjects, those who receive their prenatal care at a Baystate practice location outside of Baystate Medical Center will be offered the option of receiving study visits at their prenatal care location. The Clinical RN Study Coordinator will travel to the practice location to conduct study visits. Study drug will be dispensed at these visits in the same manner as it is dispensed at Baystate Medical Center. Study drug will be signed out from Baystate Investigational Pharmacy prior to the study visit and will be transported by the study RN to the site. The study drug will remain in the RN's possession until it is dispensed to the subject per the protocol; drug dispensing will be documented in the subject's record as well as in the study drug accountability log per protocol.

Pregnant smokers will first be identified by clinic personnel and referred to our recruiter after expressing an interest in study participation. Study sites will also utilize direct mailings and Internet advertising for recruitment purposes. Study personnel at Baystate will review CIS to assess potential eligibility of women identified in the daily appointment report of all women scheduled for OB appointments at Wesson Women's Clinic, Baystate Maternal-Fetal Medicine, Baystate Midwifery and Women's Health, Baystate Wesson Women's Group, Baystate Mary Lane, and Baystate Wing. Women identified as potential participants will be approached to determine if they are interested in participating in the study.

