1. **Randomization assignment:** As previously noted randomization will be 1:1 for nicotine inhaler or placebo assignment. To ensure comparability of subjects in the treatment groups, we will employ urn randomization, a probabilistic balancing procedure that assigns patients to conditions so that groups are balanced on key variables [57]. Key variables that we would like to balance groups on include history of preterm delivery (yes/no), gestational age at study entry (<19 weeks vs. \geq 19 weeks), and number of CPD (<10 vs. \geq 10).

The nurse will fax key variables for a given subject to the research pharmacist at UCONN who will enter these variables into a specially developed computer algorithm by that is

the basis for the urn randomization procedure. In this way, treatment groups will be comparable on important features that may influence treatment outcome. Once the pharmacist enters these variables, the computer assigns a treatment assignment. The pharmacist will communicate with the study nurse (by fax or e-mail) which medication box # to dispense to the subject.

2. **Maternal blood draw** (approximately 15 cc): Venipuncture will be performed using standard sterile blood drawing techniques by trained personnel. Serum will be separated on site and stored at -20 degrees C on at least a biweekly basis until transfer to UCHC where it will be stored at -70 C. Samples will be measured for cotinine, the major metabolite of nicotine, and a reliable measure of overall nicotine intake. Cotinine will be measured by GC/Mass Spectrometry at Yale University. UCHC Core Lab will ship transport tubes to Yale after subjects' Week 2 visit. If the subject does not come to Visit 2, the blood will be obtained at the next scheduled visit. Serum will also be measured for hydroxycotinine/cotinine ratio, the rate at which nicotine is metabolized. Samples will be shipped in compliance with DOT/IATA regulations (dry ice, Fed-Ex Overnight Express, etc.). The results will be emailed to the P.I. and the study coordinator at each site. Serum will measured for high sensitivity C-reactive protein (Siemens Medical Diagnostics, Los Angeles CA) by solid phase chemiluminescent immunometric assay and sICAM (R&D systems, Minneapolis, MN) measured by sandwich EIA in the GCRC core laboratory. If possible, this blood draw will be incorporated with other routine prenatal blood draws.
3. **Urine sample:** Urine will only be used as a backup for cotinine if necessary.

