Describe length of subject's participation in the study including number of visits, frequency of visits, and length of visits:

The subject will be in the study from the time of enrollment (13-26 weeks gestation) until 6 months after delivery. Each subject will have 10 visits. The screen and baseline visit are each 1.5 hours long. The remaining visits are approximately 45 minutes long.

Methods of Data Collection and Types of Data to be collected (may refer to attached surveys/ forms etc.)
See Attached surveys

Method(s) of data analysis:

Specific Aim 1: To compare the efficacy in pregnant smokers of the nicotine inhaler or matching placebo for smoking cessation and reduction in pregnant smokers We will first examine variation in the main outcome (7 day PPA rates at 32-34 weeks gestation) by treatment site using the intraclass correlation coefficient. If there is a difference by site, it will be used as a nesting factor in a generalized estimating equations logistic model. At the end of patient follow-up, the difference in the proportion of subjects who successfully quit smoking will be calculated along with a 95% confidence interval for the “true” difference between treatment groups. To evaluate whether randomization was effective, summary statistics for patient characteristics in the two study arms will be compared. If there is an imbalance in patient characteristics, statistical adjustment will be used to ensure that the initial results were not biased by those imbalances.

We will use a linear mixed model to evaluate the effects of the nicotine inhaler on smoking reduction or exhaled CO from baseline first to 6 weeks and then to 32 weeks gestation. Prior to these analyses, the distribution of the dependent variables, number of CPD (and exhaled CO), will be examined for normality and outliers and transformations will be performed if necessary. Treatment group and visit will be fixed factors and the intercept will be random. The model will also include a treatment-by-time interaction to test whether, over time, the number of CPD changes differentially by treatment group.

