We would be remiss if we did not also consider a mediational model that includes nicotine exposure *per se* to explain increased birth weight in an NRT trial. Wisborg et al. [7] hypothesized that in their study, it was not tobacco reduction, but an independent anti-inflammatory effect of nicotine, that increased birth weight via reduced platelet aggregation. Consistent with this statement is the fact that they found no measurable effects on tobacco reduction in their study and nicotine *per se* reduces inflammation [81, 82] and platelet aggregation [83, 84]. Evidence against this argument is that nicotine levels in two NRT pregnancy trials were similar [7] or lower in the nicotine versus placebo groups. To determine the effects of nicotine *per se* during pregnancy, we will examine effects of cotinine (independent of tobacco reduction) on pregnancy outcomes and on biomarkers.

Safety: See data and safety monitoring plan for details on safety considerations. In the case of a serious adverse event due to study treatment, the medication will be stopped and the blind may be broken by contacting research pharmacy at UCONN.

Nicotine Replacement for Smoking Cessation during Pregnancy

Retention: Efforts will be made to obtain follow-up information on all subjects regardless of adherence to treatment. Letters will be mailed prior to the telephone follow-up call. Home visits to collect follow-up data will be scheduled when necessary. We will obtain permission during the informed consent process to contact a significant other to obtain the participant's current telephone number should they change residences.

Incentives: These include parking validation, bus tokens, and lunch vouchers. Participants will be reimbursed \$20 per visit for childcare and travel expenses. The use of these incentives made it possible to collect data from 75% of subjects in our completed trial [1].

Drug Handling and Accountability: We will have study personnel (the same person who will dispense the medication) transport study medication from UCONN to Baystate or Hartford Hospital and place it in the locked cabinet. If for some reason the study nurse is unable to transport drug, a research assistant will pick up the drug and pharmacy and transport to Baystate to give to study nurse who will sign off that she received the medication. A signature log has been developed for drug transport and storage (see drug accountability log).

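### If quit rates differ by site, Aim 1 moves to a logistic GEE nested on what are most naturally two sites, with no standard error, trigger cut-off or decisive analysis named

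*Combined protocol and SAP*

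**What the plan says.** All references are to the combined protocol and SAP.

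- **Site rule** (Method(s) of data analysis, Specific Aim 1). Variation in the main outcome is examined "by treatment site using the intraclass correlation coefficient". Then: "If there is a difference by site, it will be used as a nesting factor in a generalized estimating equations logistic model". No ICC cut-off, working correlation, SE type, small-sample correction or reference distribution follows.
- **Second summary, same paragraph.** Without any condition, "the difference in the proportion of subjects who successfully quit smoking will be calculated along with a 95% confidence interval". The plan does not rank this against the GEE.
- **Sites** (Study Design & Procedures, Recruitment). "Study visits will occur at either Hartford hospital (referrals from HH clinic, CHS, or the surrounding greater Hartford area) or Baystate Medical Center". Drug Handling and Accountability also has staff "transport study medication from UCONN to Baystate or Hartford Hospital and place it in the locked cabinet". The recruitment justification names Baystate and Hartford Hospital as the sites, although there it describes the previous study. Visits at outlying Baystate practices are also allowed: such women "will be offered the option of receiving study visits at their prenatal care location".
- **Randomization** (Baseline, item 1). Women are randomized individually by urn. "Key variables that we would like to balance groups on include history of preterm delivery (yes/no), gestational age at study entry", together with cigarettes per day. Site is not listed.

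**The concern.** A nesting factor in a GEE is most naturally its cluster variable. The SE usually reported with GEE is the empirical (sandwich) one, which estimates variance from the spread between clusters and relies on having many of them. With two clusters it rests on a single contrast and is often far too small.

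The rule concerns the main outcome, and the outcome data themselves decide whether it applies. If the GEE is then taken as the test of treatment, an unstated software setting could decide whether the trial is called positive. The GEE and the unconditional CI could also give opposite answers, with nothing in the plan to choose between them.

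**Working it through.** **1. The plan's own figure.** Inputs from Sample size and justification, Aim 1: 14.9% v 26.9%, 180 per arm, two-sided 0.05. The mean rate is 0.209.

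- z = [0.12·√180 − 1.96·√(2·0.209·0.791)] / √(0.149·0.851 + 0.269·0.731)
- z = (1.610 − 1.127)/0.569 = 0.849, so power is 0.802.

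The stated 0.80 is reproduced by a plain two-proportion comparison of individually randomized women.

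**2. Closed form for two equal sites, independence working correlation.** Let d1 and d2 be the treatment log odds ratios within each site.

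- Estimate: (d1 + d2)/2.
- Uncorrected sandwich variance: (d1 − d2)²/8.
- So z = √2·(d1 + d2)/|d1 − d2|. With no treatment effect this is √2 times a t variable on 1 df.
- P(|z| > 1.96) = 1 − (2/π)·arctan(1.96/√2) = **0.398**.
- With the correction factor K/(K−1) = 2 but still a normal reference: 1 − (2/π)·arctan(1.96) = 0.300.

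**3. Simulation within the branch.** 360 women, individual 1:1 randomization, no treatment effect. Site sizes and site quit rates are assumptions, because the documents give no quit rate by site.

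| Two-site analysis | Type I error |
|---|---|
| Uncorrected sandwich, normal reference; site rates from 14.9%/14.9% to 12%/27%, splits 180/180 to 300/60 | 0.39-0.44 |
| Same, site rates 5%/35% | 0.48-0.49 |
| Model-based SE | about 0.04-0.07 |
| Sandwich with K/(K−1) and t on 1 df | about 0.05-0.06 |
| Unadjusted difference in proportions, 95% CI | 0.04-0.05 |

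Restricting to trials in which a site trigger fired does not change the sandwich figures materially. The t-corrected version has power of only 0.16-0.18 at the planned effect, against the planned 0.80. In the two-site branch the sandwich GEE and the unadjusted CI disagree in about 36-38% of null trials.

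**4. Whole procedure, two equal sites, sandwich SE, GEE decisive if triggered.** Assume a site test at p<0.05 as the trigger and error of 0.05 outside the branch.

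- No site difference: 0.05·0.40 + 0.95·0.05 = 0.068, about 0.07 (simulated 0.068).
- Site rates 10%/20%: the trigger fires in 0.758 of trials. 0.758·0.408 + 0.242·0.05 = 0.32 (0.330 when the whole procedure is simulated directly).

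The missing cut-off matters. Over the two-site settings tried (no site difference up to 10%/20%), the whole-procedure error is 0.08-0.36 with ICC > 0.01 and 0.05-0.17 with ICC > 0.05.

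**5. The alternative.** A site-stratified Cochran-Mantel-Haenszel (CMH) test was run in 24 settings of site number, size and quit rate. Type I error was 0.048-0.052 and power at the planned effect 0.77-0.81. Coverage of the Mantel-Haenszel risk-difference CI was 0.947-0.951. Test and CI disagreed in about 0.2% of null trials.

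**The case against.** The strongest reply is that the plan never commits to the analysis that fails. It names no sandwich SE. With a model-based SE the inflation essentially disappears, and a statistician who saw two clusters might well choose that. The same paragraph also promises an unconditional difference in proportions with a 95% CI, whose error is near 0.05 whatever happens in the GEE. The trigger is not wholly undefined either, since the statistic (ICC) and the outcome are named and only the cut-off is missing. Site has a clear natural reading too: outlying visits are run by the travelling Baystate coordinator with drug from Baystate's pharmacy. Calculations with seven or eight sites would be an extension of the text.

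All of that stands, and it limits the claim. A reader might infer that this trial has a 40% false-positive rate, or that 0.40 is the worst case. The documents support neither. The figure needs the branch to fire, an uncorrected sandwich SE, a normal reference and a decisive GEE. It is also not a ceiling, since it rises to 0.48-0.49 at site rates of 5% and 35%.

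The reply does not remove the open choice. Under one sentence of the plan, defensible implementations give error from about 0.05 to about 0.40, and the choice would be made after the outcome has been examined by site. A small-sample correction is no way out with two sites, because it costs most of the power. A model-based SE with an independence working correlation is in essence ordinary logistic regression, so it would not adjust for site at all.

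**Conclusion.** The point holds as a weakness of pre-specification with a potentially large consequence, and it should be fixed. The plan makes site the nesting factor of a logistic GEE when an ICC without a cut-off suggests a site difference. The natural number of sites is two, and neither the SE nor the decisive analysis is named.

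The size is conditional. Type I error is about 0.40 within the branch for plausible site differences if the uncorrected sandwich SE is used with a normal reference and the GEE decides. Over the whole procedure, with a p<0.05 trigger, it is about 0.07 with no site difference and about 0.33 at 10%/20%. It is near 0.05 with a model-based SE or if the unadjusted CI decides. Site quit rates, site split and trigger are assumptions. The closed form depends only on two equal clusters and the stated SE and reference.

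**What to change.** - Define treatment site as Hartford v Baystate, with outlying practices counted under Baystate.
- Delete the ICC trigger and the site-clustered GEE. Because randomization is individual, treat site as a stratum.
- Pre-specify one decisive Aim 1 analysis, used whatever the site results: a site-stratified CMH test, with the Mantel-Haenszel risk difference and its 95% CI from the same stratification. Logistic regression with treatment and site as fixed factors is an acceptable alternative, but one of the two should be chosen in advance.
- If the GEE is kept, the minimum is to name a model-based SE, the trigger threshold and which analysis is decisive. The choice of model would then still depend on the outcome data.

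The cost is analysis wording only. Each woman's site is already known, and no new data, visits or sample size are needed.
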